## 12. Randomisation

Patients will be randomly allocated to one of the 2 conditions using a random sequence generator such as can be found online:

(https://www.random.org/sequences/?min=1&max=66&col=3&format=html&rnd=new). The sequence can be initiated and managed by the dispensing pharmacist and schedule 1 license holder (Invicro, previously Imanova). Blinding and labelling will be done in collaboration with the manufacturing pharmacy (e.g. GSTT, Juniper and Fisher pharmaceuticals). An example of a random sequence for 2 conditions is provided below:

Condition 1	Condition 2
2	1
3	4
5	6
8	7
10	9
12	11
13	14
15	16
18	17
19	20
22	21
24	23
25	26
27	28
30	29
32	31
34	33
35	36
38	37
40	39
41	42
43	44
46	45
48	47
50	49
51	52
54	53
56	55
57	58
60	59

**Table 1.** Example of a random sequence by which patients recruited to the trial enter the relevant conditions. This sequence is held by the dispensing pharmacy (at Invicro) who do not disclose the randomisation to the study team until situations where the blind is broken.

Patient numbers will be independently monitored by InForm, the data system used by Imperial's in house Clinical Trials Unit (Imp-CTU). Versions of objective tests will be counterbalanced using the same randomisation code (e.g. to ensure a 50:50 split, versions A and B will alternate, with version A provided first). Invicro will also direct the study team as to what version of tests will be used and they will also keep their own detailed log of which patients enter which condition. The Imp-CTU system uses InForm ITM (Integrated Trial Management) System, a web-based data entry system which builds an Oracle database for each individual clinical trial.

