#### Visit 2: Scan 1/Prep

The scanning procedure takes approximately 2.5 hours, with the scan itself lasting for no longer than 90 minutes. The scan session will be followed by psychological preparation with the therapy team (two individuals) who will sit with the patient during their dosing session. Psychological preparation will take approximately 3 hours, with two breaks. This visit will take approximately **5.5 hours** in total.

#### Visit 3: Dosing session 1

The dosing session will take place the day after scan 1. Depending on the results of randomisation, the patient will receive either 25mg (conditions 1) or 1mg psilocybin (condition 2) in the morning. After their dosing session is over, they will be given either placebo capsules (condition 1) or 10mg escitalopram capsules (condition 2) to take home with them. The dosing day will typically run for ~8 hours and involve: arrival at 9am, initial preparation, including relaxation techniques. Dosing at 10:30am. Drug effects (25mg only) are typically experienced for 5-6 hours (i.e. subsiding to a low-negligible level at 3:30-4:30pm). Depending on the magnitude of residual drug effects, patients will be asked to complete questionnaires from 3:30pm onwards and take part in a filmed and audio recorded structured interview at ~4:30/5pm (consent for this is included in the consent sheet – and with consent, all visits will be filmed as default). A study psychiatrist will assess the patient for potential discharge. If the patient is to travel home, a taxi will be ordered. Patients will typically leave the study centre around 5:30/6:00pm.

[figure not shown]

Fig 2. Dosing day timeline

At the end of the first dosing session, patients will be given a course of capsules to be taken daily (upon waking) for the following 6 weeks. Randomisation will determine whether these capsules are to be escitalopram or placebo. Patients will be asked to take their first capsule as close to **8:00am** as possible the morning after the first dosing session and document exactly when it was taken, to ensure standardisation of peak plasma concentration where relevant (i.e. escitalopram condition). N.B. peak plasma concentrations of escitalopram are reached 3-4 hours post-ingestion [10]. Each patient will take one capsule each day for the first 3 weeks and two for the remaining 3 weeks, regardless of whether they are in condition 1 or 2.

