#### 5.3 Confidentiality

Patient's identification data will be required for the registration process and will be held in the screening CRF only. The research team will maintain patient confidentiality at all times. Unique, anonymous patient identifiers will be issues after screening when a patient is enrolled in the study. Identifiers will be issues in a regular ordinal manner, e.g. P1, P2, P3 etc. and these identifiers will be issued to the manager of the randomisation (Invicro, previously Imanova) to determine the relevant condition and task/test versions for each patient (see randomisation, section 12).

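### The only allocation list in the protocol is built entirely of fixed blocks of two, and its caption blurs that example with the live list

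*Protocol*

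**What the plan says.** Section 12 describes the method in one sentence: "Patients will be randomly allocated to one of the 2 conditions using a random sequence generator such as can be found online". It gives no block size or other restriction. A table follows, introduced by "An example of a random sequence for 2 conditions is provided below", which places patient numbers 1 to 60 in two columns of 30.

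The caption of Table 1 begins "Example of a random sequence by which patients recruited to the trial enter the relevant conditions" and continues "This sequence is held by the dispensing pharmacy (at Invicro) who do not disclose the randomisation to the study team", until the blind is broken. The first part calls the table an example; the second speaks of the same sequence as the one in custody.

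Other parts of the protocol bear on this:

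- Section 5.3, on numbering: "Identifiers will be issues in a regular ordinal manner, e.g. P1, P2, P3 etc".
- Section 2.6, Visit 1: each patient is allocated when eligibility is confirmed.
- Section 2.6, Visit 2: scan 1 is followed by "psychological preparation with the therapy team (two individuals) who will sit with the patient during their dosing session".
- Section 2.6, Visit 3: "Drug effects (25mg only) are typically experienced for 5-6 hours".
- Section 2.6, Visit 7, and Section 13: each patient is unblinded 6 weeks after the first dosing session.
- Section 2.1.1: patients and therapy staff are to prepare for up to 25 mg in every case, so that expectations before dosing are the same in both arms.

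**The concern.** Withholding a list from the study team protects it only if its structure cannot be guessed. Here the one structure on view sits in the protocol, which the study team works from. A reader of Table 1 would reasonably expect patients 1 and 2 to be in different arms, then 3 and 4, and so on.

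Because identifiers run in order, a patient's place in a pair can be read from the identifier. The first patient's arm becomes known formally at week 6. It may be inferred earlier, on the dosing day, because acute effects are described for 25 mg only. Under blocks of two, the second patient's arm is then fixed.

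Two things are at stake. One is allocation concealment, if the deduction can be made before the second patient's eligibility is decided. The other is the equal preparation that Section 2.1.1 relies on, if staff can deduce the arm before they prepare that patient. The protocol does not say whether the same two staff treat both patients of a pair.

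**Working it through.** **1. Table 1 as printed.** Condition 1 holds 30 numbers and condition 2 holds 30. Each of 1 to 60 appears once, which agrees with the 30 per condition in Section 4.2.1.

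**2. Its structure.** Row k contains exactly the numbers 2k-1 and 2k, one per condition, for all 30 rows. The longest run in one arm is 2. If 30 of 60 patients were assigned by an unrestricted shuffle, the chance that all 30 pairs split is

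2^30 / C(60,30) = 9.1 × 10^-9.

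Table 1 is therefore blocks of two, not the result of a plain shuffle of 1 to 60.

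**3. Upper bounds by type of list.** These assume that every earlier allocation and the block sizes are known and that the guesser picks the arm with more places left. The comparison block sizes are assumptions.

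| List | Certain allocations of 60 | Expected correct guesses of 60 |
|---|---|---|
| Blocks of 2 | 30 | 45.0 |
| Blocks of 4 | 20 | 42.5 |
| Blocks of 6 | 15 | 41.0 |
| One 30/30 shuffle | 1.9 | 34.4 |

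**4. How much could be known in time, if blocks of two are used.** The protocol gives no recruitment rate, so r = 1, 2 or 4 patients per month is assumed, with random arrivals. The number of second-patient arms known is

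k = 30 × exp(-r × g / 30.4),

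where g is the gap in days needed between the two patients. The timeline with washout is taken as allocation on day 3, preparation on day 28, dosing on day 29 and unblinding on day 71.

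| Second patient's stage, and source of first patient's arm | g | k at r = 1 / 2 / 4 |
|---|---|---|
| Before preparation, inferred at dosing | 29 - 28 = 1 | 29.0 / 28.1 / 26.3 |
| Before preparation, unblinding only | 71 - 28 = 43 | 7.3 / 1.8 / 0.1 |
| Before enrolment, inferred at dosing, with washout | 29 - 3 = 26 | 12.8 / 5.4 / 1.0 |
| Before enrolment, inferred at dosing, no washout (assumed gap) | 7 | 23.8 / 18.9 / 11.9 |

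The last row matters because Sections 2.3.3 and 2.4.1 expect unmedicated patients and Section 2.5 allows them a shorter interval without giving one.

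**5. Imperfect inference.** If the first patient's arm is inferred with accuracy a, expected correct guesses are 30 + k × (a - 0.5). Before preparation at r = 1: a = 1 gives 30 + 29.0 × 0.5 = 44.5; a = 0.9 gives 41.6; a = 0.7 gives 35.8. Simulation with the same timing gives about 34, 32 and 31 for one shuffled list, and about 40, 33 and 31 for concealed random blocks of 4, 6 and 8. The accuracies are assumptions.

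**6. Price of a shuffled list.** With N entries, half per arm, the SD of the arm difference at patient 60 is sqrt(60 × (N - 60) / (N - 1)): 2.4 for N = 66 and 3.9 for N = 80 (assumed lengths). A 34/26 split multiplies the standard error by sqrt((1/34 + 1/26) / (2/30)) = 1.009, a rise of 0.9%.

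**The case against.** The strongest reply is that Table 1 is twice called an example, no section fixes a block size for the live list, and the pharmacy already withholds it. Block details are properly kept out of protocols. This stands, and it rules out any claim that the trial was or will be allocated in pairs. It does not dispose of the point: withholding a list does not hide a structure that is printed, and the caption invites the reader to take the two as one.

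Second, the harm is limited. If inference at dosing is reliable, staff learn a patient's own arm on the dosing day under any list, and later contacts are exposed in the same way. Section 2.1.1 describes 1 mg as able to serve as an effective placebo, so inference may be far from certain. Section 11 has some preparation at screening, before allocation. The baseline QIDS is also taken at screening (Section 4.1.2), so only selection could affect it. All of this stands. Correct guesses are not bias in the QIDS, and nothing here converts one into the other.

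Three further readings are tempting but not supported:

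- The settings in the generator link (1 to 66, 3 columns) may look like an error. Sixty-six entries are compatible with 60 completers, the columns affect layout only, and the link is offered as an illustration.
- The sentence "Versions of objective tests will be counterbalanced using the same randomisation code" may suggest that test versions reveal allocation. The protocol does not say how the versions alternate, and on some readings they reveal nothing.
- The washout timeline alone suggests that the gain lies in preparation and not in selection: at 2 patients per month, pairs give 30 + 5.4 × 0.5 = 32.7 correct guesses before enrolment, against about 34 for a shuffle. With an assumed 7-day gap, pairs give about 39. The conclusion is not general.

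**Conclusion.** The point holds as a defect in what Section 12 displays and how it is captioned. The only allocation structure in the protocol is fixed blocks of two, and it is not clearly separated from the live list.

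If the live list follows it, up to 30 of 60 allocations could be deduced from the pair's first patient. That is an upper bound. The number known before preparation or enrolment may be close to that bound or close to zero. It depends on the recruitment rate, the mix and length of pre-dosing intervals, and the reliability of inference at dosing; the protocol gives an interval of about 4 weeks for washout patients and nothing firm on the rest.

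A reader might infer that half the allocations are predictable, or that a better list would secure the blind. The documents support neither: the first is conditional on the live list, and a patient's own arm may still be inferred on the dosing day. Sample size and power are unaffected. The change is worth making because it is specific, reduces a route to bias and costs almost nothing.

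**What to change.** - Delete Table 1, or state plainly that it does not show the structure of the live list. Correct the caption so that the sequence in custody is clearly a different one.
- State that the dispensing pharmacy or an independent statistician generates a new computer-randomised 1:1 list without fixed blocks of two. One shuffled list is the least predictable; randomly varying, undisclosed block sizes are an alternative that protects less if inference is near certain.
- State that the list and any block sizes are kept out of documents the study team holds, and that the list is long enough to reach 60 completers.
- As an optional precaution, take the A/B test versions from a separate list.

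The cost is protocol wording and one new list. The downside is a slight possible imbalance: a difference of 8 between arms, as in 34/26, is about 2 SDs for an 80-entry shuffle (8 / 3.9) and raises the standard error by about 0.9%.

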#### 13. Breaking of blind

In the event of a medical emergency where breaking the blind is required to provide medical care to the trial participant, the investigator will have access to a mechanism that permits rapid unblinding should they feel this is necessary. The investigator will have the ability to unblind in an emergency without first discussing this with any other trial personnel or the sponsor. Thus, the blinding code for each participant will be kept in individual sealed, tamper-proof envelopes on site, for such scenarios. Treatment assignment should remain blinded unless that knowledge is necessary to determine subject emergency medical care. The rationale for unblinding must be clearly explained in source documentation and CRF, along with the date on which the treatment assignment was obtained. If there are no emergencies throughout the trial, unblinding will happen for all patients on Follow-Up 3, 6 weeks after the first psilocybin dosing session. For the purposes of the safety database maintained by Compass Pathways and Worldwide Clinical Trials (see section 7.5 above), they will be informed of the unblinding results at the end of the trial (after the last patient, last visit).

#### 14. Significant other assessment process

We will also ask patients' significant others for brief ratings of the patient's depression symptoms before and 6 weeks after the dosing day. The Significant Other Questionnaire has 10 Likert scale items and will take approximately 10 minutes to complete. Patients and their significant other will be made aware that this is not a compulsory part of the study procedure.

The procedures for obtaining an assessment from a significant other will be as follows: at screening, the patient will be asked if they consent to us contacting their significant other (a relevant item is included in the consent form). We will ask for the name and email address of a significant other. We will contact this person by email to explain that we are seeking ratings of depression symptoms for the patient in question. At the same time, they will be sent an information sheet and consent form to consider. If they choose to consent, they will return the completed consent form to us, after which, we will email them the pre-study questionnaire. We will explain that we will contact them via email at some point in the next six months to complete another rating.

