#### 2.5 Procedures

The patient's immediate care team will be made aware of the study and will identify a patient and ask them if they are willing to be contacted by us. The primary caregiver will then inform us of any patients who are interested in participating and provide a contact telephone number and/or email. The patient will be issued with an A4 summary sheet containing a brief summary of the study and our contact details. The more comprehensive information sheet will also be made available to them. After the patient has initiated contact with us, we will inform them of the nature of the study and organise an appropriate time for an initial telephone screen. We will ask the patient if we can contact their GP/psychiatrist and this will be done via an email using a standard letter template.

Eligibility will be principally determined by the study psychiatrist who will thoroughly screen all patients to identify and confirm the presence of major depression and exclude other conditions. Supporting information from relevant mental health professionals and/or general practitioners will be sought prior to entry into the trial to confirm diagnosis and ensure that all patients meet the inclusion criteria.

If the patient appears to be eligible (post-telephone screen and post-contact with their GP/psychiatrist), a date for the first screening visit will be arranged. This will be a meeting with the study psychiatrist to review patient history, current symptoms, and to further check inclusion and exclusion criteria.

There will be around 4 weeks from first screening visit to the first study day visit to allow analysis of screening data (e.g. blood tests) to determine eligibility and enable contact to be made between their GP and/or mental health practitioners, and so that proper and cautious washout of antidepressant (4 weeks for fluoxetine and 2 weeks for other antidepressants) can be done, where applicable. If no medication washout is required, the time from screening to study day one can be shorter than 4 weeks, although we will strive to acquire weekly QIDS ratings as soon as the patient's entry into the trial is confirmed. In cases where medication washout is required, if symptoms show a marked increase in relation to the cessation/tapering

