# Visit 7 (time since first dosing session = 6 weeks/time since second dosing session = 3 weeks)

The final study visit will take place 6 weeks after the first dosing session. This visit will include a final MRI scan. Patients will arrive at 10am and be scanned at 11am. The scanning session will last for no longer than 90 minutes. After this, patients will be asked to complete some questionnaires and will take part in a structured interview in which they will be asked how they have felt today and the past 6 weeks. The HAM-D and MADRS assessments will be performed which enquire about depressive symptoms over the last week. A comprehensive side-effects questionnaire will also be completed, which asks about side-effects over a 6-week period [11]. A second ECG scan will also be conducted in order to ensure no effect of either drug on heart physiology and a repeat routine blood test will be done (see above for a complete list of tests). This visit will take approximately 5 hours in total. At the end of this visit, we will inform the patient of the condition they **were** enrolled in; thereby breaking the blind. Breaking the blind at this time point will enable us to assess treatment safety and efficacy for both conditions

and provide the patient with information on what they have received - which may then inform future decisions regarding treatment, e.g. whether or not they want to continue with escitalopram if they were in condition 2.

Study Timeline			
Date	Event	Main assessment/s	Approximate Duration
Visit 1	Screening	QIDS, HAM-D MADRS, ECG	5 hours
Visit 2	Scan 1	QIDS, HAM-D, MADRS, scan measures	5 hours
Visit 3	Dosing session 1 (DS1)	ASC, EDI, etc	8 hours
Visit 4	1-day post DS1	QIDS, interview	2-3 hours
Visit 5	Dosing session 2 (DS2)	ASC, EDI, etc	8 hours
Visit 6	1 day post DS2	QIDS, interview	2-3 hours
Visit 7	Final visit + scan 2 6-weeks post DS1	QIDS, HAM-D, MADRS interview, ECG, scan measures	5 hours

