## Behavioural tasks will include:

- Emotional processing battery [88]
- Cued autobiographical memory task (AMT) [44]
- Prediction of Future Life Events (POFLE) [45]
- Torrance Test of Creative Thinking (TTCT) [46]
- Emotional response to music [89]
- California Verbal Learning Test (CVLT) [90]
- Digit Symbol Substitution Test (DSST) [91]

The following scales will be used to measure subjective states during the dosing sessions to be filled out at the end of the dosing session:

- Ego Dissolution Inventory (EDI) [47]
- Mystical Experience Questionnaire (MEQ) [48]
- 11 Dimension Altered States of Consciousness Scale (11D ASC) [49]
- Psychotomimetic States Inventory (PSI) [50]
- Visual Analogue Scales (VAS)
- Geneva Emotional Music Scales (GEMS) [51]
- The Challenging Experience Questionnaire [52]
- The Imperial Emotional Breakthrough Inventory (EBI)
- Near-Death Experience (NDE) scale [53]
- o Ten Item Personality Inventory (TIPI) [88]

With prior consent, we will also send a patient's significant other a short questionnaire at baseline and at the 6-week end point to enquire how they perceive the patient's depression and whether they have noticed any changes in the patient's behaviour since the intervention.

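### Nothing requires the significant other's 6-week depression rating to come back before the patient is told the arm, so it can be collected unblinded even when the protocol is followed

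*Protocol*

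**What the plan says.** The timing of the informant rating appears in three sentences of the Protocol.

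- Section 2.7, after the behavioural tasks and dosing-session scales: with prior consent, the significant other receives a "short questionnaire at baseline and at the 6-week end point".
- Section 14, opening: significant others are asked for "brief ratings of the patient's depression symptoms before and 6 weeks after the dosing day".
- Section 14, end of the procedure paragraph: "We will explain that we will contact them via email at some point in the next six months to complete another rating".

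The unblinding time appears in two places.

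- Section 13: without an emergency, "unblinding will happen for all patients on Follow-Up 3, 6 weeks after the first psilocybin dosing session".
- Section 2.6, Visit 7: "At the end of this visit, we will inform the patient of the condition" to which they had been assigned.

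Section 14 also says that the questionnaire has 10 items, takes about 10 minutes, is handled by email and is voluntary.

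**The concern.** The second informant rating and the disclosure of the arm share a nominal time, week 6, and the Protocol does not say which comes first. The informant is close to the patient and answers remotely. Once the patient knows the arm, the informant may know it within hours.

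Among the measures in section 2.7, this is the only depression rating made by someone who is neither the patient nor study staff. That section says it also covers changes noticed since the intervention. Its value lies in being a separate view. An informant who knows whether the patient had high-dose psilocybin or escitalopram brings expectations about that treatment to the rating. The Protocol's background section names expectation as a possible explanation for the results of the sponsor's open-label study.

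A form returned well after week 6 has a second problem. Sections 2.1.2 and 2.5 allow treatment to change once the blind is broken, so a late rating also reflects what followed the trial period.

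**Working it through.** The Protocol states no figure to reproduce, and no sample-size or power calculation bears on the point. The check is one of sequence.

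**Step 1: the nominal times.** Count from the first dosing session as week 0.

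| Event | Time | Source |
|---|---|---|
| Second informant rating | week 6 | sections 2.7 and 14 |
| Patient told the arm | week 6, end of Visit 7 | sections 2.6 and 13 |

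The interval from the planned rating to disclosure is 6 − 6 = 0 weeks. The calendar gives no separation, so only a stated order could keep the rating blinded.

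**Step 2: is an order stated?** For the assessments made at the visit, yes. Section 2.6 describes the scan, questionnaires, interview, HAM-D, MADRS, side-effects form, ECG and blood test, and puts disclosure at the end. The informant form is not part of that visit. It goes by email to another person, and neither section 2.7 nor section 14 places it before disclosure or gives a window around week 6.

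**Step 3: what happens if the form goes out on the day?** The patient arrives at 10am and the visit lasts about 5 hours, so disclosure falls at about 10:00 + 5 h = 15:00. A form emailed that morning can be answered in time, since it needs only about 10 minutes. The same form answered that evening is answered after disclosure. Both are a 6-week rating under sections 2.7 and 14.

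**Step 4: does the six-month sentence help?** No. It says what the informant will be told about a second contact. Week 6 lies inside that span, and so does a long stretch after disclosure. It neither moves the planned time nor protects it. If it were deleted, steps 1 to 3 would stand unchanged.

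**Step 5: how many ratings are exposed?** The Protocol plans up to 60 completers and does not say how many will have an informant or how quickly forms return. Assuming one informant per patient at most, the number of ratings made after disclosure could be anything from 0 to 60. The documents do not narrow that range.

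**The case against.** The strongest reply is that the schedule is clear. Two sentences say 6 weeks, and the six-month sentence only describes an explanation given to the informant at enrolment. **This stands.** A reader might infer that section 14 contradicts itself, or that staff may request the rating whenever they like over half a year. The text does not support either reading, because a week-6 request satisfies all three sentences.

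A reader might also count how much of the six months falls after disclosure. If the period starts at screening (an assumption, as the Protocol does not say), about 4 weeks to the first study visit and 6 to 7 weeks more put disclosure at week 10 to 11. That leaves 15 to 16 of 26 weeks. This is a share of a calendar span, not a probability of a late rating, and should not be used as a measure of risk.

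A similar gap might be suspected at baseline. Section 14 says that the first rating is made before dosing and calls the form a pre-study one, so its timing is stated.

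Further replies are that the rating is voluntary, is not named among the outcomes in sections 2.2.1 and 4.1, and is given no analysis in section 10. These also stand, although the secondary list in section 2.2.1 is open-ended. They limit the weight of the point.

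Finally, informants may guess the arm anyway. Section 2.4.2 asks for a friend or relative at home after dosing, and section 2.6 attributes the hours of drug effect to the 25 mg dose only. This limits what any fix can achieve, but suspecting the arm is not the same as being told it.

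None of these replies supplies the missing order between the rating and disclosure. That order is a matter of data collection, and no later analysis can make a rating given after disclosure blinded.

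**Conclusion.** The point holds in a narrow form. The planned time for the second informant rating is week 6 and is not in dispute. Disclosure falls at the same time, and nothing requires the rating to be obtained first. Following the Protocol as written can therefore yield ratings from informants who know the arm, and the six-month wording does nothing to prevent it.

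The importance is minor. The effect is confined to one voluntary, non-primary measure, and no primary conclusion depends on it. The direction and size of any bias cannot be derived from the documents. The conclusion assumes that some patients tell their significant other the arm, and that some forms are answered after the end of Visit 7. Both are plausible, but the Protocol quantifies neither.

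**What to change.** In section 14, replace the six-month sentence with one stating that:

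1. the second form is emailed in the days before Visit 7;
2. its return is requested before the disclosure at the end of that visit;
3. each return is date-stamped;
4. any form received after disclosure is reported separately as unblinded and left out of any 6-week comparison between arms.

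Add the same timing to the sentence on the significant other in section 2.7.

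The cost is a short wording change and one scheduled email. Some ratings will be made a few days before the exact 6-week point, and a few late ones will leave the comparison. The change removes formal unblinding only. It does not stop an informant from inferring the arm from the dosing days, and any report of this measure should say so.
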